## Protocol Revision History

### Protocol Version with Summary of Changes

### Version Date

Protocol Version with Summary of Changes	Version Date
v. 1.0	06/01/2021
v. 1.1	07/01/2021
V 1.2	7/16/2021
V 1.3	8/31/2021
V 1.4	9/23/2021
V 1.5	3/17/2022
V 1.6	4/23/2022
V 1.7	5/12/2022
V 1.8	6/27/2022

## List of Abbreviations

ADA	American Diabetes Association
AE	Adverse Event
CDCES	Certified Diabetes Care and Education Specialist
CGM	Continuous Glucose Monitor
CITI	Collaborative Institutional Training Initiative
CONSORT	Consolidated Standards of Reporting Trials
CRF	Case Report Form
CV	Coefficient of Variation
DCC	Data Coordinating Center
DCCT	Diabetes Control and Complications Trial
DKA	Diabetic Ketoacidosis
DSMB	Data and Safety Monitoring Board
DSMP	Diabetes Self-Management Profile
ED	Emergency Department
FDA	Food and Drug Administration
GCP	Good Clinical Practice
GLP	Good Laboratory Practices
GMI	Glucose Management Indicator
GMP	Good Manufacturing Practices
HIPAA	Health Insurance Portability and Accountability Act
HRQoL	Health Related Quality of Life
ICH	International Conference on Harmonization
IRB	Institutional Review Board

LAR	Legally Authorized Representative
PAID	Problem Areas In Diabetes
PHI	Protected Health Information
PI	Principal Investigator
QC	Quality Control
REDCap	Research Electronic Data Capture
SAE	Serious and Reportable Adverse Events
SEDS	Self-Efficacy for Diabetes
SES	Socioeconomic Status
SMA	Shared Medical Appointment
SOC	System Organ Class
SOP	Standard Operating Procedures
T1D	Type 1 Diabetes
T1DAL	Type 1 Diabetes and Life
TAR	Time Above Range
TBR	Time Below Range
TIR	Time In Range

## Protocol Summary

**Title:** Group Visits to Improve Technology Use, Glycemic Control, and Quality of Life in High Risk Children with Type 1 Diabetes

**Brief Summary:** We propose to conduct a prospective cohort pilot study to assess the impact of SMA visits in underserved youth with poorly controlled T1D. The trial will employ an enrollment visit, SMA visits every 3 months over a 12 month study period, followed by a 6-month observational period to assess feasibility and acceptability of SMA and the impact on glycemic control, self-management skills, and health related quality of life.

**Study Population:** Inclusion criteria are: ages 8-12, T1D duration of at least 1 year, at least one A1C value > 8% in the past year, Black race and/or Latinx ethnicity, public health insurance, and English fluency in the youth and parent.

**Study Site(s):** This study will be conducted entirely at Children's National Hospital and Specialty Care Locations

**Number of Participants:** 20 parent-child dyads (40 participants)

**Accrual Ceiling:** 20 parent-child dyads (40 participants)

**Study Duration:** 18-24 months

**Subject Duration:** 18 months

**Objective(s):** **Primary Objective:** To evaluate the feasibility and acceptability of SMA among underserved youth with T1D as measured by recruitment, CGM initiation, retention, satisfaction surveys, and semi-structured interviews.

**Secondary Objectives:** To evaluate the preliminary impact of SMA on glycemic control, self-management skills, self-efficacy, diabetes related quality of life, and treatment satisfaction among underserved T1D youth

**Methodology:** Prospective cohort pilot study

**Outcome Measures:** **Primary Outcome:** Feasibility as assessed by recruitment, (>60% of reached/ eligible participants), CGM initiation (>80%), SMA sessions attended (>80%), and study retention (>80%). Acceptability as assessed by user satisfaction surveys (>80%), perceived utility of the intervention content, and perceived benefits from participation (>80% reporting satisfaction and perceived utility).

**Secondary Outcomes:** Differences in the following within subject measures across the SMA intervention and during the follow-up period: 1) CGM time in range from 70-180 mg/dL (TIR), 2) time below range (< 70 mg/dL) (TBR), 3) time above range ( $\geq$  180 mg/dL) (TAR), 4) mean sensor glucose, 5) coefficient of variation (CV) of glucose, 6) CGM wear time, 7) episodes of DKA, 8) episodes of severe hypoglycemia, 9) ED visits, hospital admissions, 10) A1c, 11) qualitative measures exploring self-management, satisfaction, health related quality of life [Type 1 Diabetes and Life (T1DAL), Diabetes Self-Management Profile (DSMP), Self-Efficacy for Diabetes (SEDS), Problem Areas in Diabetes (C-PAID), CGM Benefits and Burdens].

**Study Intervention/  
Procedures:**

Secure REDCap surveys will be completed either ahead of or at each visit by patients and caretakers. During intervention SMA visits, the facilitator role will be shared by a pediatric endocrinologist, certified diabetes care and education specialist (CDCES), nutritionist, and psychologist. SMA sessions will consist of facilitator led-discussions, and youth and caregivers will individually meet with the endocrinologist at different time points during the session. Patient CGM data will be analyzed 2 weeks ahead of visits, and we will summarize self-management skills, health-related quality of life measures, and treatment satisfaction at each intervention visit.

**Statistical Analysis:**

CGM data will be analyzed using library GLU in R.73 using mixed effect models. The independent variables will be baseline time in range, child age, and a random subject effect to account for correlation of measurements on the same subject. Interaction terms of age and baseline time in range with the intervention will explore possible effect modification ( $p < 0.10$ ) of these characteristics. Differences in participant self-management skills and patient satisfaction will be reported as mean Likert scale score and standard deviation. Similar analysis using linear longitudinal

regression analysis will be conducted. Results will be reported as least-squares means (LSMEANS) with standard errors. Casewise deletion will be used to handle missing data.

## Study Design Schematic

**Table 1.** Schedule of study procedures.

Construct	Measure	Initial SMA	3mo SMA	6mo SMA	9mo SMA	12mo SMA	15mo	18mo
14-Day CGM Markers of Glycemic Control	Mean CGM Glucose	X	X	X	X	X	X	X
	Coefficient of Variation	X	X	X	X	X	X	X
	Glycemic Mgmt Indicator (GMI)	X	X	X	X	X	X	X
	CGM Wear Time	X	X	X	X	X	X	X
	CGM TIR	X	X	X	X	X	X	X
	CGM TBR	X	X	X	X	X	X	X
	CGM TAR	X	X	X	X	X	X	X
A1c		X	X	X	X	X	X	X
Youth Surveys	T1DAL	X	X	X	X	X	X	X
	DSMP	X	X	X	X	X	X	X
	SEDS	X	X	X	X	X	X	X
	PAID	X	X	X	X	X	X	X
	CGM Ben & Bur	X	X	X	X	X	X	X
	SMA Evaluation	X	X	X	X	X	X	X
Parent Surveys	P-T1DAL	X	X	X	X	X	X	X
	P-DSMP	X	X	X	X	X	X	X
	P-SEDS	X	X	X	X	X	X	X
	P-PAID	X	X	X	X	X	X	X
	CGM Ben & Bur	X	X	X	X	X	X	X
	SMA Evaluation	X	X	X	X	X	X	X
Semi-Structured Dyad Interview						X		

## **Section 2: Introduction, Background Information and Scientific Rationale**

### **2.1 Background Information and Relevant Literature**

There are significant disparities in type 1 diabetes (T1D) care and outcomes. Hemoglobin A1c (A1c) levels and rates of acute and chronic T1D complications are highest among publicly insured youth and those from racial-ethnic minority groups and low socioeconomic status (SES). CGM use has been associated with improved glycemic control and health related quality of life in youth with T1D, however rates of uptake and sustained use are lowest among racial and ethnic minority youth and those from lower income households. SMA have shown great promise for improving glycemic control, self-management skills, and self-efficacy in adolescents with T1D, but have not been specifically developed to meet the needs of underserved youth. We aim to develop SMA specifically designed to meet the needs of racial, ethnic, and socioeconomically underserved youth in order to address disparities in T1D care and outcomes.

We are including relevant preliminary data that supports the individual components proposed in the current intervention, including the need to include diverse populations in CGM research, key intervention components of promoting positive quality of life factors around diabetes management, and the positive impact that SMA can have on underserved diabetes patients and their caretakers.

Health disparities among type 1 diabetic patients: Health disparities exist among individuals with T1D of different races and ethnicities, with minorities having worse long-term outcomes compared to non-Hispanic whites in the U.S. Minority youth with diabetes are significantly more likely to have higher A1C levels, elevated cardiovascular risk factors, early signs of kidney disease, retinopathy, and neuropathy as compared to non-Hispanic white youth. Black/African American and Hispanic youth remain woefully underrepresented in diabetes technology trials. Unfortunately, this mirrors the reality of real-world clinical care: non-Hispanic Black and Hispanic youth are much less likely to use CGMs as part of T1D management, and worse, those who are not using these technologies report that they have not been offered the option to use these treatment modalities. Using data from the T1D Exchange, Agarwal and colleagues reported that 72% of non-Hispanic White young adults (ages 18-25) used CGM as compared to 18% of non-Hispanic Black youth and 40% of Hispanic Youth. The source of health disparities in T1D technology access and use are complex and multifaceted. Targeted, evidence-based support for technology use and psychosocial functioning must address multiple systems and be responsive to the needs of diverse youth with T1D. However, diabetes distress and lower rates of diabetes technology use are modifiable barriers that are critical to address according to the tenets of social cognitive theory, which recognizes that knowledge, self-efficacy, and psychosocial factors all impact health behaviors and outcomes. Interventions rooted in this theory hold the potential to address barriers in attaining health equity among youth with T1D.

Health related quality of life in people living with T1D : Health related quality of life (HRQoL) has become a fundamental focus of comprehensive healthcare. Impaired

HRQoL has been found in children and adolescents with several chronic conditions, including diabetes. Chronic disease during childhood can result in more frequent depressive moods and other negative emotions, lower life satisfaction, poorer school performance, and negative self-esteem and self-concept. Having diabetes requires many behavior changes, which can lead to stress in both the patients and their families, and studies have shown that adolescents with diabetes have a lower life satisfaction and health perception than healthy adolescents. Diabetes-specific emotional distress and quality of life are psychosocial variables that are strongly associated with key diabetes outcomes, such as adherence and metabolic control. Social support from classmates and caretakers, as well as adaptation and coping skills are key to improving medical outcomes.

Benefits of CGM therapy: CGMs are minimally invasive devices that use a subcutaneous sensor to report and record changes in interstitial glucose values every 5 minutes to 15 minutes. This technology can alert patients to hypoglycemia and hyperglycemia and also allows them to make diabetes treatment decisions without the need for a confirmatory fingerstick blood glucose level. Improvements in the accuracy and usability of CGM, better insurance coverage, and greater acceptance by both clinicians and patients have led to dramatic increases in the use of this technology over the past decade. In 2011, just 6% of all patients in the United States Type 1 Diabetes Exchange (T1DX) registry were using CGM as compared to 27% in the period from 2016-2018. Continuous glucose monitor (CGM) use among youth with T1D is recommended whenever possible, and has been associated with decreased hypoglycemia and severe hypoglycemia, improvement in A1c, and improved quality of life and treatment satisfaction.

Positive effects of SMA in diabetes: The American Diabetes Association (ADA) recommends that education and social support is continually offered to youth and their caregivers at routine clinic visits, however this is challenging within the constraints of the current clinical care model. Shared medical appointments (SMA), wherein small groups of patients participate in group education sessions in place of traditional clinic visits, have been successfully employed in pediatric chronic disease management, and are well suited for diabetes care. SMA visits allow additional time for interprofessional self-management education, skill building, self-efficacy, and peer support. Specifically in pediatric T1D, SMA has been shown to allow for discussion of a greater breadth of topics while also placing greater focus on behavioral and psychosocial needs. Adolescents participating in SMA exhibit improved glycemic control and reduced diabetes distress through the development of a supportive community. Increased satisfaction with follow up care can also translate into improved attendance and engagement in regularly scheduled clinical care. However, to date, the use of SMA has not been well-studied in underserved youth and has not been used specifically to promote uptake and sustained use of diabetes technologies.

## **2.2 Scientific Rationale**

The primary aim of this pilot study is to assess the impact of a 12-month SMA model employing interprofessional facilitator-mediated discussion to promote the uptake and

sustained use of CGM, while also providing peer support, and fostering community in order to improve glycemic control and promote health equity among youth with T1D. Although SMAs have been used in T1D, few have been designed specifically to improve health equity by addressing the needs of diverse youth and their families. This proposed intervention will be developed to meet the needs of non-Hispanic Black and Latinx youth with public insurance. Furthermore, this SMA will be the first specifically developed to support uptake and sustained use of diabetes technology among youth who have been historically least likely to access these technologies.

We expect that the SMA model will lead to high rates of SMA retention and satisfaction, greater CGM wear time and sustained use, improved glycemic control, and improved diabetes specific quality of life, self-management behaviors, and self-efficacy scores compared to patients in the traditional individual appointment model. The interprofessional model incorporating CDCES, psychology, and nutrition will allow for youth and caregivers to interact with the entire diabetes care team and will also allow for sufficient time to focus on both education and strategies to cope with the psychosocial burdens and challenges needed to optimize adherence and outcomes. Lessons learned from this comprehensive interprofessional SMA will also provide insights that will allow for development of additional strategies needed to promote equal opportunity for all youth to achieve health and quality of life targets without being hindered by race, ethnicity, or socioeconomic status.

We propose to recruit up to 20 underserved children with poorly controlled T1D and their primary diabetes caregiver. Inclusion criteria are: ages 8-12, T1D duration of at least 1 year, at least one A1c value  $\geq 9\%$  in the past year, Black race and/or Latinx ethnicity, public health insurance, and English fluency in the youth and parent. For the purposes of this study, because non-Hispanic black and Latinx youth with public healthcare insurance are the least likely to have access to CGM technology, we will use the term underserved to specifically refer to this population.

Primary and secondary outcomes will be evaluated at baseline, 4 follow-up points during the SMA intervention, and 3 and 6 months after the final group visit. A 3-month interval for SMA and assessment was chosen to correspond to standard clinical follow up visit schedule. Participant data will be matched by age, race, insurance status, duration of diabetes, in the routine follow up model, in order to evaluate the impact of SMA on the outcomes of interest.

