### **3.4 Secondary Outcome Measure(s)**

Secondary outcomes will include CGM metrics and chart review that can be used to assess effects on glycemic control, and survey measures designed to explore potential psychosocial benefits, including changes in self-management skills, self-efficacy, treatment satisfaction, and diabetes related quality of life. We will look at differences in the following measures from baseline to completion of the SMA intervention, as well as 3 and 6-months after completion of the SMA intervention: 1) CGM time in range from 70-180 mg/dL (TIR), 2) time below range (< 70 mg/dL) (TBR), 3) time above range ( $\geq$  180 mg/dL) (TAR), 4) mean sensor glucose, 5) coefficient of variation (CV) of glucose, 6) CGM wear time, 7) episodes of DKA, 8) episodes of severe hypoglycemia, 9) ED visits, hospital admissions, 10) A1c, 11) qualitative measures exploring self-management, satisfaction, health related quality of life as measured with the following validated questionnaires (T1DAL, DSMP, SEDS, C-PAID, CGM Benefits and Burdens scale).

CGM time in range from 70-180 mg/dL (TIR) has been correlated with A1c values, which have classically been used as primary outcomes in T1D studies because of their association with microvascular complications. This connection to long-term complications also makes TIR a better primary outcome measure than survey measures because this data has greater potential to alter real-world prescribing practices than patient perceptions captured by questionnaire. We have chosen to focus on TIR rather than A1c because of the propensity for A1c variation in Non-Hispanic Black youth who also have a higher propensity for hemoglobin variants.

Additional CGM derived measures of glycemic control are commonly used outcomes in studies of T1D technology. A1c has been included because it has classically been considered the gold standard. The acute complications of T1D being examined are also frequently used in T1D studies. The survey measures exploring quality of life are among the most widely accepted outcome measures in their specific topic areas.

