## **Section 4: Study Design**

Dyads of youth with T1D aged 8-12 years and their primary diabetes caretakers identifying as non-Hispanic Black or Latinx will be recruited to participate in a prospective cohort pilot study exploring feasibility and acceptability of SMA and the impact on glycemic control, self-management skills, and health related quality of life. This trial will employ an enrollment visit, SMA visits every 3 months over a 12-month study period, and a follow-up 6-month observational period to continue to evaluate outcomes once patients return to routine individual follow up care. The study will include a single intervention group participating in the SMA visits (n=20).

All staff participating in the SMA visit will receive comprehensive training on how to facilitate the SMA discussion sessions effectively. All topics that will be covered at each SMA visit will be reviewed by the study staff ahead of the visit. Potential participants will

be screened for participation using our electronic medical records system and will be approached during routine clinical visits. After explaining all study procedures, informed consent using an IRB-approved consent form will be obtained for all participants. After obtaining consent, a blinded Dexcom G6 CGM will be placed on the participant. Participants will be instructed to wear the blinded CGM for 10 days in order to obtain baseline glycemic control data prior to starting the SMA visit intervention. At the completion of the 10 day wear period, participants will mail back the blinded CGM in a pre-addressed envelope so that the data can be assessed within 30 days of the wear time. Because SMA visits will be used in place of routine clinic visits and because participants will not require any additional in person study visits, we anticipate significant interest in participation with minimal barriers. Secure REDCap surveys will be sent to participants via email 1 week before each follow-up visit. If the surveys have not been completed at the time of the visit the participant will be asked to complete the measures using an iPad or paper in clinic at the time of their visit. Youth who elected not to use a CGM for routine clinical care, will be asked to wear a blinded professional CGM for 10 days prior to each visit whenever possible.

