SMA Structure: SMAs will consist of 4-6 underserved youth with T1D and their primary diabetes caregiver. All youth and caretakers will complete standard check-in procedures with the clinic medical staff, including routine clinical intake questionnaires, vital sign assessments and point-of-care fingerstick A1c measurements. Before each session, dyads will be invited to submit questions to the research team that will then be anonymously reviewed and discussed among the group during the SMA. In the event that no questions are submitted by families, the facilitator will begin the discussion with stories and questions related to technology use and potential barriers in order to focus the discussion on the aspect of diabetes management being highlighted in that specific SMA. After discussing the questions, the facilitator will lead a group discussion focusing on the topic of the day. During each visit, the facilitator role will be shared by a pediatric endocrinologist, CDCES, nutritionist, and psychologist. Youth and caregivers will individually meet with the endocrinologist at different time points during the session to update personal management plans and goals of care. The group visit will conclude with a review of the core concepts discussed. Youth will be encouraged to set and share individual goals to be addressed before the next SMA.

Enrollment visit: This visit will occur at a routine clinic visit once a patient expresses interest in participating in the study. Alternatively, patients expressing interest in enrolling who are unable to do so at a routine clinic visit will have the option to come back for enrollment at a different time. A study team member will meet with the patient and family to review the study details and obtain consent. Randomization will be completed after consent has been obtained. A blinded Dexcom G6 pro CGM will be placed on the patient and be worn for 10 days in order to collect baseline data prior to starting the intervention. Phone applications that will allow for sharing of CGM data between patients and the diabetes clinical care team will be downloaded and established before the end of the visit.

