## **6.3 Study Interventions and Follow-Up**

### Enrollment visit

Those who have met eligibility criteria and express interest in study participation will meet with study staff to review the study specifics in more detail and obtain consent. Randomization will occur after consent has been obtained. A blinded Dexcom G6 pro

CGM will be placed on the patient and be worn for 10 days in order to collect baseline data prior to starting the SMA intervention. Phone applications that will allow for sharing of CGM data between patients and the diabetes clinical care team will be downloaded and established before the end of the visit.

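### The protocol describes three designs, but Section 8 supports only within-child change, which should not be reported as the impact of SMA; Hypothesis 2a and the event rates lack an informative baseline

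*Combined protocol and SAP*

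**What the plan says.** **Design.** Section 4 states: "The study will include a single intervention group participating in the SMA visits (n=20"). The same section, under the enrollment visit, says "Randomization will be completed after consent has been obtained", and Section 6.3 repeats it: "Randomization will occur after consent has been obtained". No arms, ratio or method are given. Section 2.2 adds that "Participant data will be matched by age, race, insurance status, duration of diabetes, in the routine follow up model" and expects better "self-efficacy scores compared to patients in the traditional individual appointment model".

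**Aim.** Section 2.2 says "The primary aim of this pilot study is to assess the impact of a 12-month SMA model", whereas Section 3.1 makes feasibility and acceptability the primary objective.

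**Contrast.** The Protocol Summary defines secondary outcomes as "Differences in the following within subject measures across the SMA intervention and during the follow-up period". Section 3.4 says "We will look at differences in the following measures from baseline to completion of the SMA intervention", and also at 3 and 6 months afterwards. Section 8.2 tests 12 months against baseline only.

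**Models.** The Protocol Summary, Section 6.4 and Section 8.4 list baseline time in range (TIR), child age and a random subject effect, plus interactions of age and baseline TIR with the intervention. Sections 6.4 and 8.4 say the models measure the intervention's impact on glucose control. Section 8.1 says there will be no formal SAP, so no further document settles these points.

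**Baseline.** Section 5.2 excludes CGM use within 60 days of enrolment. A blinded sensor is placed at enrolment for 10 days (Section 4), and Table 1 schedules CGM wear time at the initial SMA. Children who do not use CGM, or who stop, are asked to wear a blinded sensor for 10 days before visits (Sections 4 and 6.3). Event chart review is described from the initial visit onward (Section 6.3) and by interval before each visit (Section 6.4).

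**The concern.** Read together, the sections could lead one team to randomize, another to extract matched controls, and a third to do neither. A reader of Section 2.2 would expect a routine-care comparison that has no control source, number or analysis.

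The labelling matters for a second reason. Section 2.4 says the results should inform later randomized studies. A before-after change reported as the impact of SMA could be mistaken for the effect of SMA over routine care. Children enter without CGM, want to start it (Section 5.1) and are taught it at the first SMA (Section 6.3), so the two begin together.

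Two secondary analyses would also give results that mean little if followed as written: the test of sustained CGM use against baseline, and the comparison of event rates.

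**Working it through.** **1. What each design could detect.** The plan gives no power calculation to reproduce; Section 8.5 justifies up to 20 dyads as a pilot. Assuming two-sided 5% and 80% power, t-based minimum detectable effects are:

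| Reading | Comparison | Detectable effect |
|---|---|---|
| Single group | 20 children against own baseline | 0.66 SD of change |
| Matched routine care | 20 v 20 (control number assumed) | 0.91 SD |
| Randomized | 10 v 10 (equal split assumed) | 1.32 SD |

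The three readings are materially different studies.

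**2. Model as listed.** With only baseline TIR, age and a random subject effect, no coefficient represents change from baseline to 12 months, which is what Section 8.2 tests. The intervention does not vary between children in one group, so an interaction with it cannot be estimated between children. With a categorical visit term, change is estimable.

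**3. Hypothesis 2a, personal use.** Baseline is 0 of 20 at enrolment. Every change is then from non-use to use, and the exact two-sided McNemar test (assumed) gives p = 2 × 0.5^k for k users at 12 months.
- k = 5: p = 0.0625.
- k = 6: p = 0.031. That is 6/20 = 30% (exact 95% CI 12% to 54%), far below the plan's own 80% benchmark for CGM initiation.
- The chance of at least 6 of 20 users is 0.58, 0.87 or 0.98 if true use is 30%, 40% or 50%, whatever the reason for use.

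**4. Hypothesis 2a, any use.** If blinded wear counts, assigned wear alone gives 10/14 = 71% of the two-week window to a child who does not use CGM. The enrolment sensor could do the same at baseline if its wear falls in that window. Use is then driven by the protocol at both ends.

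**5. Event rates.** With 20 children followed throughout, the SMA year gives 20 person-years and the post-SMA half-year 10. Exact Poisson limits are chi-square(0.025, 2x)/2 and chi-square(0.975, 2x+2)/2, divided by person-years.
- 2 events in 20: 10 per 100 person-years (1.2 to 36).
- 1 event in 10: also 10 (0.3 to 56).
- Linear analysis of the first case: two children at 100 and eighteen at 0 give mean 10, SD 30.8, SE 30.8/√20 = 6.88, and 95% CI 10 ± 2.093 × 6.88 = −4.4 to 24.4. The lower limit is an impossible rate.

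**6. Precision of within-child change.** Half-width = t(0.975, 19) × SD/√20. For TIR with an assumed SD of change of 15 points: 2.093 × 15/4.472 = 7.0 (4.7 to 9.4 for SD 10 to 20). For A1c with an assumed SD of 1.5: 0.70 (0.47 to 0.94 for SD 1.0 to 2.0). Groups of 5 with an assumed intraclass correlation of 0.05 to 0.10 multiply these by √(1 + 4 × ICC), giving at least 7.7 to 8.3 and 0.77 to 0.83.

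**7. Illustration of attribution, all inputs assumed.** Suppose SMA adds nothing, CGM start raises TIR by 10 points, the SD of change is 15, and 18%, 40% or 80% would have started CGM anyway. The first two rates are use in young adults (Section 2.1), so a rough guide only; the third is the initiation benchmark. Expected change is 1.8, 4.0 or 8.0 points. The 95% CI lies above zero in 7%, 20% or 62% of 20-child trials, against 2.5% with no change. Over gains of 5 to 15 points and SDs of 10 to 20, the ranges are 4–21%, 6–72% and 13% to nearly 100%.

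**The case against.** The strongest reply is that this is a pilot. Its primary outcome needs no control, secondary effects are called preliminary, and the randomization sentences look like leftover text. Promoting CGM uptake is the stated purpose of the SMA (Section 2.2), so CGM start may be a pathway of the intervention and not a confounder. Sections 6.4 and 8.4 mention differences between time points, so the missing visit term looks like a drafting gap. All of this stands. But calling an effect preliminary limits the strength of a claim, not what is compared, and leftover text at the consent visit still has to go.

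Four stronger readings are tempting and the documents do not support them.
- **That the Hypothesis 2a baseline is simply zero.** This is exact only for personal CGM use at enrolment. Table 1 schedules wear time at the initial SMA, after a study-placed sensor.
- **That regression to the mean explains the change.** Baseline TIR and A1c are measured afresh after the qualifying A1c, so at most some residual remains, and its size is unknown.
- **That baseline event rates are impossible to obtain.** Chart review before the first SMA is not excluded; its look-back is just not stated.
- **That a TIR effect size will be carried into a later trial.** Section 2.4 says only that the results will inform design.

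**Conclusion.** The concern holds for the secondary analyses and the design text; the feasibility and acceptability outcome is unaffected. The design conflict and the omitted visit term are plain on the page and rest on no assumption. Within-child change is a legitimate quantity once visit is in the model. However, it mixes SMA, CGM start, time and possibly residual regression to the mean, and these data cannot separate them.

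Hypothesis 2a is uninformative on either reading of use: 6 of 20 users would reject (test assumed), or assigned wear supplies up to 71%. Change from baseline in event rates is undefined as written, and with 20 and 10 person-years only description is realistic. The TIR scenario shows the mechanism and is not an estimate for this trial. These points should be corrected, but they do not undermine the pilot.

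**What to change.** 1. Delete the randomization sentences in Sections 4 and 6.3.
2. Delete the matched and individual-appointment comparisons in Section 2.2. If they are kept, specify control source, number, matching and analysis in Section 8.4.
3. In the Protocol Summary and Sections 6.4 and 8.4, model change from baseline at each post-baseline visit, with categorical visit, the baseline value of that outcome and child age as fixed effects and a random subject effect. Replace interactions with the intervention by interactions with visit, labelled exploratory. Report change at 12, 15 and 18 months with 95% CIs, described as change after starting SMA and CGM and not attributable to SMA alone. State that the intervals ignore clustering by SMA group and may be too narrow.
4. Align the impact wording in the Protocol Summary and Sections 2.2, 3.2, 4, 6.4, 8.2 and 8.4 with that description.
5. For Hypothesis 2a, replace the test against baseline with the number and percent using personal CGM at 12 months, with an exact 95% CI and excluding assigned blinded wear. Report personal wear time descriptively by visit.
6. For events, replace linear regression with counts, number of children with at least one event, and rates per 100 person-years with exact CIs for the SMA and post-SMA periods. Note that repeat events in one child make Poisson intervals too narrow. State that chart review runs to month 18. Add a stated pre-SMA look-back only if change from baseline is wanted.
7. Reconcile the Sub-Group Analyses text, which sets age and race/ethnicity aside, with the age terms in Section 8.4 and with the acceptability breakdown by age and race/ethnicity in Sections 3.3, 6.4 and 8.4.

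**Cost:** wording edits, one model term and slightly more analysis work, with no new visits or participants. The efficacy statement becomes more modest. A look-back or a specified comparator would need extra chart extraction and possibly IRB permission.
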